2 LIST OF ABBREVIATIONS

Term	Definition	Term	Definition
ACTH	Adrenocorticotrophic hormone	FDA	Food and drug administration
ADT	Antidepressant therapy	GCP	Good clinical practices
AE	Adverse event	GGT	Gamma glutamyltransferase
ALP	Alkaline phosphatase	GPCRs	G-protein coupled receptors
ALT	Alanine aminotransferase	HAM-A	Hamilton anxiety scale
AST	Aspartate aminotransferase	HAM-D	17 items Hamilton depression scale
ATRQ	Antidepressant treatment response questionnaire	HDL	High density lipoprotein
AVP	Arginine vasopressin	HIPAA	Health insurance portability and accountability act
BMI	Body mass index	HIV	Human immunodeficiency virus
bpm	Beats per minute	HPA	Hypothalamus-pituitary-adrenal
BUN	Blood urea nitrogen	HS-CRP	High sensitivity C-reactive protein
C	Cortical cataract	IATA	International air transport association
CFR	Code of federal regulations	ICF	Informed consent form
CGI-I, S	Clinical global impression-Improvement, -Severity	ICH	International conference on harmonization
Cl	Chloride	IL	Interleukin
C_{max}	Maximum plasma concentration	IRB	Institutional review board
Con Med	Concomitant medication	IUD	Intrauterine device
CPK	Creatine phosphokinase	IWRS	Interactive web response system
CRA	Clinical research associate	K	Potassium
CRF	Corticotropin-releasing factor	kg	Kilograms
CRF	Case report form	LC-MS/MS	Liquid chromatography-tandem mass spectrometry
CRO	Clinical research organization	LDH	Lactate dehydrogenase
C-SSRS	Columbia suicidality severity rating scale	LDL	Low density lipoprotein
CTNI	Clinical trials network and institute	LOCS	Lens opacities classification system
CV	Curriculum vitae	LogMAR	Logarithm of the minimum angle of resolution
CYP	Cytochrome P450	MAD	Multiple ascending dose
DMP	Data management plan	MADRS	Montgomery Asberg depression rating scale
DNA	Deoxyribonucleic acid	MCH	Mean corpuscular hemoglobin
DSM	Diagnosis and statistical manual of mental disorders	MCHC	Mean corpuscular hemoglobin concentration
ECG	Electrocardiogram	MCV	Mean corpuscular volume
eC/PRO	Electronic clinician and patient rated outcome	MDD	Major depressive disorder
ECT	Electroconvulsive therapy	MDMA	3,4-methylenedioxy-N-methylamphetamine
EDTA	Ethylenediaminetetraacetic acid	MedDRA	Medical dictionary for regulatory activities
EOT	End of treatment	MGH	Massachusetts general hospital
ET	Early termination	MINI	MINI-International neuropsychiatric Interview
ETDRS	Early treatment diabetic retinopathy study	mg	Milligrams

[figure not shown]
Term	Definition	Term	Definition
Mg	Magnesium	RDW	Red cell distribution width
mL	Milliliter	RO	Receptor occupancy
mmHg	Millimeter of mercury	rpm	Revolutions per minute
MMRM	Mixed model repeated measures analysis	rTMS	Repetitive transcranial magnetic stimulation
MS	Medical services	SAD	Single ascending dose
msec	Milliseconds	SAE	Serious adverse event
Na	Sodium	SAP	Statistical analysis plan
NDA	New drug application	SDQ	Symptoms of depression questionnaire
NC	Nuclear color	sec	Seconds
NESS	New England survey systems	SGOT	Serum glutamic-oxaloacetic transaminase
NO	Nuclear opalescence	SGPT	Serum glutamic-pyruvic transaminase
P	Posterior subcapsular cataract	SNRI	Serotonin norepinephrine reuptake inhibitor
PCP	Phencyclidine	SOP	Standard operational procedure
PET	Positron emission tomography	SSRI	Selective serotonin reuptake inhibitor
PD	Pharmacodynamics	THC	Tetrahydrocannabinol
PGx	Pharmacogenomics	TNF-α	Tumor necrosis factor alpha
PHI	Protected health information	V_{1a}	Vasopressin 1a
PK	Pharmacokinetics	V_{1b}	Vasopressin 1b
PO	Per os	V₂	Vasopressin 2
QTcB	Bazett's corrected QT interval	WBC	White blood cell
QTcF	Fridericia's corrected QT interval	WHO	World health organization
RBC	Red blood cell		

3 SYNOPSIS

[figure not shown]
Protocol Title	A Multicenter, Randomized, Double-blind, Placebo-controlled Study of the Safety and Efficacy of TS-121 as an Adjunctive Treatment for Patients with Major Depressive Disorder with an Inadequate Response to Current Antidepressant Treatment
Protocol Number	TS121-US201
Phase of Development	2a
Number of Study Sites	Approximately 25 US sites
Study Drug	TS-121: An oral, investigational new drug with antagonistic activity of the vasopressin 1b receptor (V _{1b} receptor)
Indication	Major Depressive Disorder (MDD)
Number of Patients	
Approximately 180 randomized male and female MDD patients between 18 and 65 years of age inclusive
 
 • Placebo Group: 60 patients • TS-121 10 mg Group: 60 patients • TS-121 50 mg Group: 60 patients
Objectives	
Primary Objectives
 
 • To evaluate the safety and tolerability of TS-121 compared to placebo in MDD patients • To evaluate the efficacy of two dose levels of TS-121 compared to placebo on MDD symptoms in MDD patients 
Exploratory Objective
 
 • To evaluate the effectiveness of biomarkers in predicting TS-121 response with retrospective stratification of patients via baseline values of HPA axis and inflammatory biomarkers
Safety assessments	
Safety and tolerability will be assessed from the time the patient is administered the investigational product through the final study procedure.
 
Safety variables for assessment will include:
 
 • Adverse events • Physical examination • Columbia Suicide Severity Rating Scale (C-SSRS) • Body weight • Vital signs

	
 • Clinical laboratory tests (hematology, biochemistry and urinalysis) • 12-lead electrocardiogram (ECG) • Ophthalmological examinations
Efficacy assessments	
Primary Endpoint
 
 • Change in MADRS total score from Visit 3 (Baseline) to Visit 6 (EOT) 
Secondary Endpoints
 
 • Changes from Visit 3 (Baseline) to Visit 6 (EOT) for CGI-S, SDQ, and HAM-A total scores • Percentage of CGI-I improvers (“Very much improved” or “Much improved”) • Percentage of MADRS responders ($\geq 50\%$ reduction in total score)
Pharmacodynamic and Pharmacokinetic assessments	
Exploratory Endpoints
 
 • Pharmacokinetic data from Visit 6 may be explored relative to study results (mental health assessments and/or laboratory values) • Change from Visit 3 (Baseline) to Visit 6 (EOT) for plasma copeptin and inflammatory markers (TNF-α, IL-1, IL-6, HS-CRP) • To evaluate the effectiveness of biomarkers in predicting TS-121 response with retrospective stratification of patients via baseline values of HPA axis and inflammatory biomarkers consisting of: 
 ○ Hair cortisol ○ Salivary cortisol ○ Urine cortisol ○ Plasma copeptin, and ○ Inflammatory markers (TNF-α, IL-1, IL-6, HS-CRP)

Study Design:

Schedule of PD Marker Collection:

* : Visit 3 only
** : Visit 3 and 6

Study Design and Procedures

This multicenter study is comprised of a screening period of up to 4 weeks, with a 2-week single-blind placebo lead-in period followed by a 6-week randomized, double-blind, placebo-controlled treatment period with a 2-week follow-up period, comparing the safety, efficacy, pharmacokinetics, and exploratory pharmacodynamics of TS-121 to placebo as an adjunctive treatment for patients with MDD. Patients must remain on the same single antidepressant (SSRI, SNRI or bupropion) for 6 weeks, and fixed dose for 4 weeks prior to Visit 1.1. Patients will remain on their current antidepressant therapy (ADT) with a fixed dose throughout the course of the study.

Visit 1 (Screening): Patients will visit the site for screening assessments and an initial review of study requirements. In addition to confirming the diagnosis of MDD by MINI, a trained site rater will employ the 17-items Hamilton depression scale (HAM-D), which will be subsequently confirmed through an additional HAM-D assessment conducted by a central rater (Visit 1.1) prior to a 2-week placebo lead-in period. Patients will schedule a phone call for central rater assessments.

Visit 1.1 (Screening): The central rater will contact the patient as scheduled, and will administer the Massachusetts General Hospital Antidepressant Treatment Response Questionnaire (MGH ATRQ) for assessment of current ADT, adequacy of duration and dose of prior and current ADT, as well as degree of improvement. The central rater will also complete the HAM-D assessment and SAFER inventory for confirmation of placebo lead-in eligibility. Results will be communicated to the site prior to Visit 2.

Visit 2 (Start of Placebo Lead-In): Following initial eligibility confirmation, qualified patients will return to the site initiating a 2-week, single-blind placebo lead-in period. Patients will be instructed to take 3 capsules of investigational product (placebo) once-daily in the morning and to maintain their current ADT regimen for two consecutive weeks. Patients will download AiCure software to their smart phone or receive an AiCure device that will monitor medication adherence during the 2-week placebo lead-in period (and for the duration of the 6-week treatment period) using AiCure's interactive mobile device technology. An ophthalmologist will conduct a thorough eye examination (including slit lamp under mydriasis). Patients will be provided with supplies and instructions for at-home collection of saliva and urine for exploratory HPA axis assessment. Patients will schedule another phone call for central rater assessments (Visit 2.1), and Visit 3 will be scheduled.

Visit 2.1 (End of Placebo Lead-In): Response to placebo will be assessed using HAM-D by a central rater via phone. Results will be communicated to the site prior to Visit 3. The current HAM-D score and change in HAM-D score from Visit 1.1 to Visit 2.1 will be used to determine eligibility.

Visit 3 (Baseline): After completing the placebo lead-in period, patients will return to the site for baseline evaluations. Outpatient biological samples will be collected. Laboratory, safety and efficacy assessments will be performed. Placebo lead-in dosing compliance will be assessed. Following confirmation of eligibility, patients will be randomly assigned to receive TS-121 10 mg, 50 mg, or placebo in a 1:1:1 ratio. Patients will be instructed to continue taking investigational product once-daily in the morning and to maintain their current

ADT regimen. Visit 4 will be scheduled.

Visits 4 (Week 2): Patients will return to the site for safety and efficacy assessments. Drug accountability and dispensing of a new supply of investigational product will be performed. Compliance with the dosing schedule will be assessed. Visit 5 will be scheduled.

Visit 5 (Week 4): Patients will return to the site for safety and efficacy assessments. Drug accountability and dispensing of a new supply of investigational product will be performed. Compliance with the dosing schedule will be assessed. Visit 6 will be scheduled, which includes an ophthalmological examination.

Visit 6 (Week 6): Patients will return to the site for end-of-treatment safety, efficacy, pharmacokinetic, and exploratory pharmacodynamic assessments. Final drug accountability will be performed. Visit 7 will be scheduled, which includes an ophthalmological examination.

Visit 7 (Follow-up): Patients will return to the site for a follow-up evaluation of safety and efficacy assessments approximately two weeks after Visit 6.

4 BACKGROUND INFORMATION

4.1 Introduction

Depression is ranked as the leading cause of disability worldwide by the World Health Organization (WHO Fact Sheet No. 369; Oct. 2012). In particular, major depressive disorder (MDD) is a psychiatric illness that is characterized by the occurrence of one or more major depressive episodes, along with an absence of any history of manic, mixed, or hypomanic episodes. It is a serious, often recurrent medical condition, which is associated with a 15.9% lifetime risk of suicide attempt (Chen, 1996). Results of the World Mental Health Survey Initiative (2011) found that the average lifetime incidence of DSM-IV major depressive episodes was 14.6%, with a 12-month prevalence of 5.5% in higher income countries (Bromet, 2011).

Stress has also been hypothesized to be a pivotal factor in the pathophysiology of depression, specifically by way of the hypothalamus-pituitary-adrenal (HPA) axis, which appears to be a prominent mechanism by which the brain reacts to both acute and chronic stress through feedback loops involving several neuroendocrine hormones, including adrenocorticotrophic hormone (ACTH) and cortisol. In addition, both corticotropin-releasing factor (CRF) and arginine vasopressin (AVP) both of which are produced in the paraventricular nucleus of the hypothalamus (Vale, 1981; Aguilera, 2000), are considered primary factors in the regulation of HPA axis activity. Receptor subtypes for these neuropeptides, which may be involved in the regulation of HPA axis activity, have attracted much attention as potential targets for the treatment of depression and anxiety.

Despite the availability of numerous pharmacological and psychological treatment options, fewer than 50% of all patients with depression show full remission with optimized treatment, including trials on numerous medications with and without concurrent psychotherapy (Rush, 2006). Thus, there is a clear need for efficacious and well-tolerated agents to treat and prevent recurrent episodes of depression, and current research continues to investigate novel molecular and cellular mechanisms of depression.

TS-121 (drug substance code [REDACTED]) is an investigational new drug with antagonistic activity of the vasopressin receptor 1b (V_{1b} receptor), which plays a role in the modulation of stress and mood. Based on nonclinical studies conducted by Taisho Pharmaceutical Co., Ltd. Research Center (Japan), TS-121 appears to be a promising candidate for clinical development with a novel mode of action that may benefit MDD patients.

4.2 Mechanism of Action of Vasopressin Receptor 1b (V_{1b} Receptor)

AVP, a cyclic nonapeptide, together with CRF, are principal factors in the regulation of ACTH release from the anterior pituitary (Aguilera, 2000), and have been reported to play an important

[REDACTED]

[REDACTED]

[REDACTED]

[REDACTED]

[REDACTED]

[REDACTED]

4.4.2 Summary of Clinical Findings

Three Phase 1 studies, a single ascending dose (SAD) study (TS121-US101), a multiple ascending dose (MAD) study (TS121-US102), and a positron emission tomography (PET) receptor occupancy study (TS121-US103) have been conducted. Overall, 78 healthy male and female adult subjects were administered TS-121 to date. A top dose of 50 mg for 10 days was deemed safe and well tolerated. There were no deaths or serious adverse events reported in any of the studies.

Treatment emergent ventricular arrhythmias have been reported following single and multiple dose administrations of TS-121.

No safety trends were observed in clinical laboratory, vital signs, or physical examinations. In consideration of the nonclinical findings at the time of the MAD study, comprehensive eye examinations were performed; no abnormalities in the eyes relating to lens opacity were reported, including at the highest dose level of 50 mg for 10 days.

Additional details are described in Sections 8 and 9 of the Investigator's Brochure.

4.4.3 Known and Potential Risks to Human Subjects

Though the relevance to human subjects is not yet fully understood, nonclinical findings suggested that potential risks include cataract, hepatotoxicity, effects on the gastrointestinal system and effects on the renal system. To date, no apparent trends related to these potential risks were noted in the clinical studies.

Treatment emergent ventricular arrhythmias have been reported following single and multiple dose administrations of TS-121. During the SAD study (TS121-US101), two subjects exposed to 2.5 mg of TS-121 had defined intervals of ventricular arrhythmias while on telemetry. Plasma levels were approximately 50% of C_{max} values (40 to 70 ng/mL). The events were without symptoms, resolved without intervention, and produced no residual effects. The events were considered mild in intensity and possibly related to the study drug. One subject was discontinued from the trial, and one subject completed the trial.

In the MAD study (TS121-US102), one subject showed a single episode of 4 consecutive premature ventricular contractions without symptoms while on telemetry approximately 15 hours

after receiving 50 mg dose of TS-121 on Day 9. The investigator assessed the episode as a clinically significant event and described the event as mild and possibly related to TS-121. The subject completed the trial with no additional events.

In a PET receptor occupancy study (TS121-US103), no abnormal ECG results were reported following single TS-121 doses of up to 50 mg. See Sections 8 and 9 of the Investigator's Brochure for additional information.

4.5 Study Rationale

This multicenter study is comprised of a screening period of up to 4 weeks, with a 2-week single-blind placebo lead-in period followed by a 6-week randomized, double-blind, placebo-controlled treatment period with a 2-week follow-up period, comparing the safety, efficacy, pharmacokinetics, and exploratory pharmacodynamic effects of TS-121 to placebo as an adjunctive treatment for patients with MDD. To assess for primary effect of TS-121 vs. placebo, patients must remain on the same ADT for 6 weeks, and fixed dose for 4 weeks prior to screening. Patients will remain on their current antidepressant treatment and dose throughout the course of the study.

The study employs multiple quality attributes to reduce placebo response and to monitor patient compliance. Placebo response in MDD trials is well documented. The study employs a 2-week placebo lead-in to enrich the population with placebo non-responders. Additionally, to reduce investigator bias, a central rater assessment will be employed during the screening and the placebo lead-in periods to evaluate initial eligibility and to assess placebo response by use of the HAM-D. Furthermore, central raters will remain involved in the trial with oversight of the MADRS instrument during the treatment period. Patient compliance with dosing will be assessed during the placebo lead-in through completion of the trial by use of AiCure platform of real-time dose monitoring.

TS-121 is postulated to work primarily through the HPA axis. Biomarkers for HPA axis will be assessed at Visit 3, prior to randomized treatment administration, to assess potential screening and/or stratification factors in future trials. There is insufficient predictive knowledge of MDD patients' HPA axis biomarkers and MDD patient response to V1b receptor antagonist. Therefore, a post-hoc exploratory analysis may be conducted comparing patient response to baseline patient profiles.

██████████ is a high affinity antagonist for the human vasopressin receptor 1b (V1b receptor) that has been shown to work in a number of animal models for depression, suggesting that TS-121 may be a useful treatment option for individuals experiencing MDD. TS-121 dose selection was based on accumulated experience from preclinical studies and three previous clinical trials. The SAD study (TS121-US101) and MAD study (TS121-US102) provide safety and tolerability

support for the current doses. [REDACTED]

[REDACTED]

[REDACTED]

[REDACTED]

5 STUDY OBJECTIVES

5.1 Primary Objectives

- To evaluate the safety and tolerability of TS-121 compared to placebo in MDD patients
- To evaluate the efficacy of two dose levels of TS-121 compared to placebo on MDD symptoms in MDD patients

5.2 Exploratory Objective

- To evaluate the effectiveness of biomarkers in predicting TS-121 response with retrospective stratification of patients via baseline values of HPA axis and inflammatory biomarkers

6 STUDY DESIGN

6.1 Study Design

[figure not shown]

Figure 1. Study Design

6.2 Randomization Procedure

A subject number will be assigned to each patient at the time of informed consent at each site. At Visit 3 (Baseline), following completion of the 2-week placebo lead-in, patients who continue to meet all entry criteria will be assigned a randomization number by IWRS. A patient cannot be assigned more than one randomization number. Patients will retain their subject and randomization numbers for the duration of the study.

Each eligible patient at Visit 3 will be randomly assigned to receive either TS-121 10mg, 50mg or placebo in a ratio of 1:1:1. The kit number dispensed by IWRS will correspond to the assigned treatment.

Treatment assignments of patients will be held by IWRS throughout the study.

6.3 Blinding

To maintain the blind, matching placebo capsules will be provided for the TS-121 capsules. The placebo lead-in period will be single-blind for patients. Following completion of the placebo lead-in period, the treatment period will be double-blinded (neither the investigator nor the patient will have knowledge of the treatment assignment). The sponsor and CRO study personnel, including those involved in monitoring, data management and data analysis will also

be blinded to the treatment assignment during the trial.

6.4 Unblinding

The randomized investigational product administered to each patient will not be known to the patient or to study site personnel, except for:

- Designated IWRS personnel including study-independent personnel from the CRO (if applicable)
- Designated personnel for drug packaging
- The bioanalytical laboratory performing the PK analysis

Under normal circumstances, the blind should not be broken until all patients have completed the study and the database has been locked and finalized. The blind may be broken if specific emergency treatment would be indicated by knowing the treatment status of the patient. The blind may also be broken for events of clinical significance (see Section 11.3). In the event that the sponsor decides to break the blind for events of clinical significance, the sponsor must inform the investigator of the unblinding. The date, time and reason for the unblinding must be documented in the study source records and recorded on the CRF. If data are unblinded, access to the unblinded data should be limited to maintain data integrity of the study. Additional details will be described in the safety plan.

6.5 Early Discontinuation

Patients may discontinue study participation at any time in this trial. All randomized patients who prematurely discontinue participation after receiving at least one dose of investigational product will return to the site for an Early Termination Visit as early as possible after discontinuation, and separately, for a follow-up visit approximately 14 days after their last dose. Patients who discontinue prior to randomization at Visit 3 will be considered screening failures. If discontinued once entering the placebo lead-in period at Visit 2 but prior to randomization, discontinued patients will be required to undergo a physical examination and completion of the C-SSRS before being discharged from the study.

7 STUDY POPULATION

7.1 Study Population

This study will screen approximately 300 patients and randomize approximately 180 MDD patients. These patients are defined by the inclusion and exclusion criteria described in the following sections.

7.1.1 Inclusion Criteria

Patients must meet all of the following criteria to be eligible for enrollment:

1. Adult males and females between 18 and 65 years of age inclusive (at time of initial informed consent)
2. Patients with a current diagnosis of MDD by DSM-5, confirmed through a structured interview using MINI
3. Patients who receive the same antidepressant (SSRI, SNRI or bupropion monotherapy) for the current episode for at least 6 weeks of continuous treatment prior to Visit 1.1 and at least 4-weeks on a fixed dose prior to Visit 1.1 (the dosing duration and appropriateness of the dosage will be confirmed at Visit 1.1 by the central rater using MGH ATRQ)
[Note: Patients who currently receive 2 or more antidepressants are excluded with exception of Trazodone (≤ 50 mg/day) for sleep as outlined in Section 8.3. Fluvoxamine is prohibited as it is a moderate CYP 3A4 inhibitor (see exclusion criterion #14 and Appendix 1)]
4. Patients willing to remain on the same primary ADT and fixed dose throughout the course of the study
5. Patients who meet the total score on the HAM-D as listed below (as determined by Site or Central Raters):
 - HAM-D ≥ 18 at Visit 1 (Site)
 - HAM-D ≥ 18 at Visit 1.1 (Central)
 - HAM-D $\leq 25\%$ improvement from Visit 1.1 to Visit 2.1 (Central)
 - HAM-D ≥ 18 at Visit 2.1 (Central)
6. Patients who are rated as eligible based on the SAFER Inventory conducted at Visit 1.1
7. Female patients of childbearing potential must agree to use one of the accepted barrier methods of contraception (listed below) during the study (including the screening period prior to receiving trial medication), for at least 90 days following the last dose.
 - condom (male or female) with spermicide
 - diaphragm or cervical cap with spermicide and condom (male)

[Note: Oral contraception, vasectomy of the partner and IUD alone are not considered sufficient contraception. One of the aforementioned barrier methods listed above must be used. Females who are not currently sexually active must also consent to use one of these accepted methods of contraception should they become sexually active while participating in the study.]

Female patients of non-childbearing potential must be either surgically sterile or post-menopausal (absence of *spontaneous* menses for 12 consecutive months)

Male patients with partners of childbearing potential must agree to use appropriate and effective measures of contraception (e.g., condom plus diaphragm with spermicide; condom plus spermicide) and/or refrain from donating sperm from Visit 2 and for at least 90 days following the last dose.

8. Body Mass Index (BMI) ≥ 18 and ≤ 38 kg/m² at Visit 1 using the following formula:
weight (kg) / [height (m)]²
9. Patients who are able and willing to provide written informed consent and authorization for protected health information disclosure in accordance with Good Clinical Practice
10. Patients who are able to read, speak and understand English

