11.2 Serious Adverse Event Reporting

11.2.1 Definition of Serious Adverse Event

A serious adverse event (SAE) is an untoward medical occurrence that at any dose:

- results in death (Note: Death is an outcome and not an event and the cause of death should be listed as the SAE);
- is life-threatening (i.e., the patient was at immediate risk of death from the AE);
- requires inpatient hospitalization or prolongation of existing hospitalization;
- results in persistent or significant disability/ incapacity; or
- is a congenital anomaly or birth defect (in the child of a patient who was exposed to the investigational product)

Any other important medical event that may result in death, be life-threatening, or require hospitalization, may be considered a SAE when, based upon appropriate medical judgment, the event may jeopardize the patient and may require medical or surgical intervention to prevent one of the outcomes listed above.

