- If a death occurs and an autopsy is performed, a copy of the autopsy report should be obtained if possible when it becomes available. All efforts must be undertaken to obtain follow-up information promptly.

Any SAEs occurring from first administration of investigational product through 30 days after last administration must be reported. All SAEs will be reported, whether or not they are deemed to be related to study product. Timely reporting of SAEs will be followed in accordance with regulatory requirements as outlined in the Safety Plan.

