11.5 Pregnancy Reporting

If a patient does become pregnant during the course of the study, the patient should be discontinued immediately. The site must report all pregnancies to [REDACTED] via email or telephone within 24 hours of receiving the report of pregnancy. The site should record and maintain all relevant information on the appropriate study form, including the follow-up and outcome of the pregnancy.

Pregnancy itself is not regarded as an AE/ SAE. Congenital abnormalities/birth defects and spontaneous miscarriages should be reported and handled as SAEs. Elective abortions without complications should not be handled as AEs. The outcome of all pregnancies (spontaneous miscarriage, elective termination, ectopic pregnancy, normal birth or congenital abnormality) should be followed up and documented even if the patient was discontinued from the study (with the patient's consent).

Male patients should refrain from fathering a child or donating sperm during the study and for at least 90 days following the last dose. Pregnancy of the patient's partner is not considered to be an AE; however, the outcome of all pregnancies should be followed up and documented if possible.

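### Male inclusion criterion 7 can be met by agreeing only not to donate sperm, because it joins contraception and no sperm donation with 'and/or'

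*Protocol*

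**What the plan says.** The male part of inclusion criterion 7 (Protocol Section 7.1.1) is mandatory and opens with "Male patients with partners of childbearing potential must agree to use appropriate and effective measures of contraception". After examples of methods it adds a second undertaking, not to donate sperm, and links the two with 'and/or': "contraception (e.g., condom plus diaphragm with spermicide; condom plus spermicide) and/or refrain from donating sperm from Visit 2 and for at least 90 days" after the last dose.

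The female part of the same criterion offers no such choice. Women of childbearing potential have a short list of barrier methods, and the note to the list says "One of the aforementioned barrier methods listed above must be used".

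Section 11.5 returns to men: "Male patients should refrain from fathering a child or donating sperm during the study and for at least 90 days following the last dose".

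**The concern.** An entry criterion should admit only people who accept the precaution it sets out. This one is addressed to men whose partners could become pregnant, and contraception is the only one of its two undertakings that bears on that partner. Sperm donation is a separate matter. With 'and/or', a site that screens strictly against Section 7.1.1 has to pass a man who declines contraception but agrees not to donate. It would equally pass a man who uses contraception but keeps the option to donate.

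At stake is a partner pregnancy during the period in which the protocol itself asks men to take precautions. This is a participant-protection point. It has no bearing on the sample size, the primary endpoint or any analysis.

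**Working it through.** The check is mainly textual, and the plan gives no figure to reproduce.

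**Step 1. Who qualifies under each wording** (a man with a partner of childbearing potential)

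| Agrees to contraception | Agrees not to donate sperm | Meets criterion with 'and/or' | Meets criterion with 'and' |
|---|---|---|---|
| Yes | Yes | Yes | Yes |
| Yes | No | Yes | No |
| No | Yes | Yes | No |
| No | No | No | No |

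The third row is the problem. The usual reason for allowing an 'or' is that a man without such a partner needs only the donation undertaking. That reason does not apply, because the sentence is already limited to men who have such a partner.

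**Step 2. Comparison with the rest of the protocol**

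- Section 11.5 tells men to refrain from fathering a child or donating sperm. To refrain from one thing or another is to refrain from both, so 11.5 asks for both where criterion 7 accepts either.
- The verb differs. Criterion 7 says 'must agree'; 11.5 says 'should'. The binding text is therefore the looser one.
- 11.5 sits in a reporting section, does not name contraception, and is not among the entry criteria.
- The female part of criterion 7 has no alternative to a listed barrier method. Exclusion 16 also bars women who intend to become pregnant within 90 days of the last dose. No exclusion bars a man who intends to father a child in that period.

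**Step 3. How long the criterion runs**

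Inputs:
- Start: Visit 2, Day 1 (Section 9.1 schedule). Randomized dosing starts only on Day 16, but the criterion counts from Visit 2.
- Last dose: taken as the Visit 6 day, the last expected dosing day in SAP Section 6.1.4. Visit 6 is Day 57, with a window of ±3 days (Sections 9.1 and 9.3).
- After the last dose: at least 90 days (criterion 7).

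End of period = day of last dose + 90:
- nominal: 57 + 90 = Day 147
- early edge of the window: (57 − 3) + 90 = 54 + 90 = Day 144
- late edge of the window: (57 + 3) + 90 = 60 + 90 = Day 150

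The span is Day 1 to about Day 147, or about Day 144 to Day 150 with the window. It is shorter for a man who stops treatment early.

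**Step 4. How many men**

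This cannot be calculated. The documents do not give the share of men, the share of men with a partner of childbearing potential, or the share who would decline contraception.

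**The case against.** The strongest reply is that criterion 7 does not stand alone. Section 11.5 makes the intent plain, and exclusion 29 lets a site turn away anyone unable to meet study requirements. An investigator who reads all three has grounds to exclude a man who will not avoid conception. This is a fair point about practical risk and it stands to that extent. It does not change the criterion: 11.5 says 'should', exclusion 29 is generic and concerns ability, and neither names contraception as a condition of entry.

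A second reply is that stricter rules for women are reasonable, since they would carry the pregnancy, and that the human risks listed in Section 4.4.3 (cataract, liver, gastrointestinal and renal effects, ventricular arrhythmia) include no reproductive or male-mediated risk. Parts of Section 4 are redacted, so the importance of the male precaution cannot be judged from the visible text. That also stands. The point therefore rests on the mismatch between criterion 7 and 11.5 and does not assert a known hazard to partners.

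A reader might also infer that birth defects would go unreported, because Section 11.2.2 says "Any SAEs occurring from first administration of investigational product through 30 days after last administration must be reported" and does not mention pregnancy. The documents do not support this. Section 11.2.1 includes among serious events one that "is a congenital anomaly or birth defect (in the child of a patient who was exposed to the investigational product". Section 11.5 says "Congenital abnormalities/birth defects and spontaneous miscarriages should be reported and handled as SAEs" and sets no end date. It also says "The site must report all pregnancies to [REDACTED] via email or telephone within 24 hours of receiving the report of pregnancy", and asks for outcomes to be followed after discontinuation with the patient's consent. The sections can be obeyed together. What is missing is a cross-reference, and the requirement itself is present.

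**Conclusion.** The point holds as a defect in the wording of one mandatory entry criterion. Taken literally, the male part of criterion 7 admits a man with a partner of childbearing potential who has not agreed to contraception, and it is looser than the protocol's own instruction in 11.5. The wording governs Day 1 to about Day 147, assuming nominal visits and a last dose on the day of Visit 6.

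The practical consequence is probably small, because 11.5 shows the intent and most sites would be likely to apply it. No number of affected men can be stated. Two further inferences are not supported: that pregnancy outcomes are not collected, for the reasons given above, and that men are not told to use contraception, since the consent text is not available for review. The change is still worth making because it is specific, nearly free and brings the criterion into line with 11.5.

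**What to change.** In the male part of inclusion criterion 7, change 'and/or' to 'and', and place the period so that it clearly governs both undertakings: effective contraception and no sperm donation, each from Visit 2 until at least 90 days after the last dose.

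The cost is one wording change in a protocol amendment, with matching consent text if that does not already say so, and the loss of an occasional male candidate who declines contraception. It needs no extra visit, test or data collection.

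Two optional housekeeping edits could go into the same amendment, though the point does not depend on them. Section 11.2.2 could refer to 11.5 for pregnancy outcomes in patients. The reference in 9.2.6.5 to Section 11.4, which covers worsening of depression, should be to 11.5. Partner outcomes can stay as 11.5 has them, followed up where possible.
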